Hypertrophic scars occur mainly as a result of the tension exerted on wound edges. Tension can, directly and indirectly, lead to hypertrophic scars. BoNT A works by inhibiting the release of acetylcholine in the neuromuscular junction which indirectly causes neuromuscular transmission, leading to muscle paralysis and thus reducing wound tension. As a result of this and other mechanisms, BoNT A can be used not only as treatment but also as prevention of hypertrophic scars. BoNT A may directly modulate the activity of fibroblasts by altering apoptotic, migratory, and fibrotic pathways on pathological scars and thus improve their appearance (Kasyanju Carrero et al., 2019).

3.1: Transdermal iontophoresis:

Iontophoresis is a method of introducing ionized and neutral drugs into the skin by using an electric current. As shown in (Fig. 1), during iontophoresis, electromigration and electroosmosis are the principal mechanisms of enhancing drug transport across the skin into the systemic circulation. Electromigration refers to the ordered movement of ionized drug molecules in the presence of the applied electric field. Therefore, charged drugs are forced across the skin by electronic repulsion of similar charges. Cationic drugs can permeate through the skin by using a positively charged working electrode. Similarly, anionic drugs can cross skin by negatively charged electrodes. Electroosmosis is the fluid moving in a direction in the presence of electric field, forming an electroosmotic flow and driving the movement of hydrated ions. At physiological pH, skin has a slight negative charge. Thus, electroosmotic flow occurs from anode to cathode (Wang et al., 2021).

Fig. (1): A schematic diagram of iontophoretic technique (Adapted from Wang et al., 2021).

3.2: Factors influencing iontophoretic process:

There are various factors affecting iontophoresis as: The drug used should be water-soluble, of low dosage and susceptible to ionization. Smaller particles are more mobile. Increasing drug concentration results in greater drug delivery, but only to some extent. If buffer ions are present, they compete with the drug, reducing its delivery. The effect of iontophoresis also depends on the tissue on which the electrodes are applied (e.g., thickness, permeability, the presence of pores). In the skin, sweat glands are the most significant way the charges are carried **(Karpiński., 2018).**

3.3: Iontophoretic device:

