Is the scar painful ? Is the scar itching? No, as normal skin Is the color of the scar different? Is the scar more stiff_? Is the thickness of the scar different	0 0 1 0 70	2 0 2 0 0 0	3 0 3 0 0	4 0 4 0 0 0	5 0 5 0	6 0 6 0	7 0 7 0 0	8 0 8 0 0	9 0 9 0	10 0 10 0 0 0	Yes, worst imaginable Yes, very different
Is the scar painful ? Is the scar itching? No, as normal skin Is the color of the scar different? Is the scar more stiff_? Is the thickness of the scar different Is the scar irregular?	0 0 1 0 ?0 0	2 0 2 0 0 0 0	3 0 3 0 0 0 0 0	4 0 4 0 0 0 0	5 0 5 0 0	6 0 6 0 0	7 0 7 0 0 0	8 0 8 0 0 0	9 0 9 0 0	10 0 10 0 0 0 0	Yes, worst imaginable Yes, very different
Is the scar painful ? Is the scar itching? No, as normal skin Is the color of the scar different? Is the scar more stiff_? Is the thickness of the scar different Is the scar irregular?	0 1 0 ?0 0	2 0 2 0 0 0 0	3 0 3 0 0 0 0 0	4 0 4 0 0 0 0	5 0 5 0 0	6 0 6 0 0	7 0 7 0 0 0 0	8 0 8 0 0 0	9 0 9 0 0 0	10 0 10 0 0 0 0	Yes, worst imaginable Yes, very different +

(Adapted from Draaijers et al., 2004).

3.2-Therapeutic procedures:

3.2. (a) Procedures of iontophoretic device (Ibrahim et al., 2021):

Iontophoretic drug delivery system (Phoresor IIAuto,Model PM850, IOMED). The active electrode is placed directly over the marked area. The dispersive electrode was applied to the skin 6 inches distal from

Approved date: 17/5/2022

the active electrode (Figure 3). The dose required is selected on the device; depending on the subject's tolerance, the current intensity is gradually increased, ranging from 2 to 4 mA.

3.2. (b) -Procedures of Botox iontophoresis (Elhefnawy et al., 2016) An intralesional injection of botulinum toxin type A (Botox Allergan [®], Irvine, CA, USA).

- 1. 100 U vacuum-dried powder in a single-use vial for reconstitution diluted in 2 mL of sterile, preservative-free 0.9% saline to constitute a solution at a concentration of 4 U/0.1 mL) will be administered once a month for a total period of three months.
- 2. The dose will be adjusted to 2.5 U/cm2 of the lesion.
- 3. The dose shouldn't exceed 100 units per session.

3.2. (c) Physical therapy program for both groups:

Positioning:

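### The Botox preparation does not add up: 100 U in 2 mL is 5 U/0.1 mL, not 4, and using both written figures applies 3.125 instead of 2.5 U/cm² for scars up to 32 cm²

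*Combined protocol and SAP*

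**What the plan says.** The preparation appears twice in Chapter III: under 2.2.(b) Botulinum toxin type A (equipment) and under 3.2.(b) Procedures of Botox iontophoresis (the treatment instruction for Group A). Both places give the same three figures. The product is "100 U vacuum-dried powder in a single-use vial for reconstitution", and it is "diluted in 2 mL of sterile, preservative-free 0.9% saline to constitute a solution at a concentration of 4 U/0.1 mL".

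Section 3.2.(b) then sets the dose in units: "The dose will be adjusted to 2.5 U/cm2 of the lesion". It adds a ceiling: "The dose shouldn't exceed 100 units per session". Treatment is given once a month for three months.

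Nothing else in the document gives another vial size, another diluent volume, or a rule for converting units to millilitres. The document also does not say how many vials may be opened in a session.

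**The concern.** Vial content, diluent volume and concentration are tied together by one division, so any two of them fix the third. Here the third does not match the other two.

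This matters because the drug is a neurotoxin dosed by scar area. Every scar below 40 cm² needs less than a full vial (100 U / 2.5 U/cm² = 40 cm²), so someone must turn units into a volume at each session. The only concentration printed for that step is wrong for the only diluent volume printed. Staff who take both figures at face value would apply more than the planned dose. If different staff resolve the conflict in different ways, the applied dose per cm² would vary within Group A for a reason unrelated to the scar.

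**Working it through.** **Inputs** (sections 2.2.(b) and 3.2.(b)): vial 100 U; diluent 2 mL; stated concentration 4 U/0.1 mL; dose 2.5 U/cm²; cap 100 U per session.

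**1. The stated concentration cannot be reproduced.**
- Concentration = vial content / diluent = 100 U / 2 mL = 50 U/mL = 5 U/0.1 mL. The stated figure is 4 U/0.1 mL; the ratio is 5/4 = 1.25.
- For 4 U/0.1 mL (40 U/mL) to be right, the diluent would have to be 100/40 = 2.5 mL, or the vial would have to hold 40 × 2 = 80 U. Neither appears in the document.

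**2. Two volumes follow for the same dose.**
- From vial and diluent: 2.5 / 50 = 0.050 mL/cm².
- From the stated concentration: 2.5 / 40 = 0.0625 mL/cm².

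**3. Dose applied if both written figures are used** (2 mL diluent, volume computed at 4 U/0.1 mL).
- 0.0625 mL/cm² × 50 U/mL = 3.125 U/cm²; 3.125 / 2.5 − 1 = +25%.
- The 2 mL of solution is used up at 2 / 0.0625 = 32 cm². Above that, a single vial limits the dose to 100 U, and the excess is 100/(2.5 × area) − 1 until the cap is reached at 40 cm².

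| Scar area (cm²) | Planned units | Volume at 4 U/0.1 mL (mL) | Units applied, one vial | U/cm² applied | Excess |
|---|---|---|---|---|---|
| 10 | 25 | 0.625 | 31.25 | 3.125 | +25% |
| 20 | 50 | 1.25 | 62.5 | 3.125 | +25% |
| 32 | 80 | 2.00 | 100 | 3.125 | +25% |
| 36 | 90 | 2.25 (2.00 available) | 100 | 2.78 | +11.1% |
| 40 | 100 | 2.50 (2.00 available) | 100 | 2.50 | 0% |

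The areas are illustrative, because the document gives none. For a 20 cm² scar, three sessions would total 3 × 62.5 = 187.5 U against a planned 150 U.

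**4. If a second vial were opened** to make up the computed volume, the 25% excess would continue above 32 cm². A nominal 100 U would be 2.5 mL × 50 U/mL = 125 U, above the protocol's own cap.

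**5. Sample size.** The calculation does not use the dose. Its stated result reproduces: effect size 0.7636, two-sided α 0.05 and 38 per group give power 0.9074.

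**The case against.** The arithmetic slip cannot be defended; the argument is about its reach.

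- **The binding instruction is in units.** The protocol prescribes U/cm² and a unit cap and never prescribes a volume. Staff who treat the vial as 100 U in 2 mL dose correctly, and so do staff who dilute to 2.5 mL and dose at 4 U/0.1 mL. The excess needs staff to combine the two incompatible figures without checking, although they stand in one sentence and a single division exposes the conflict. This stands: the 25% is conditional, and zero is a realistic lower end. What can be said against it is limited. Up to 32 cm² the solution would not run short, so supply gives no warning, and the error is repeated in two sections.
- **The second vial is speculative.** The text describes a single-use 100 U vial and a 100-unit cap, so needing more than one vial should itself raise a question. This also stands; the 125 U figure is only what would follow under that assumption.
- **The number of patients is unknown.** For scars of 40 cm² or more, one full vial is the planned dose and the discrepancy has no effect on units. Without scar areas, the share of Group A below that size cannot be estimated.
- **Applied is not delivered.** The literature review (Chapter II, 3.2) says of iontophoresis: "Increasing drug concentration results in greater drug delivery, but only to some extent". The current also varies with tolerance from 2 to 4 mA. A 25% difference in applied units cannot be turned into an effect on scars or on safety from this document.
- **The preparation is attributed to a cited study.** Whether the slip came from there cannot be checked here. That is a reason not to guess which figure is wrong, but it does not make the instruction consistent.

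These points limit the size of the problem. They do not remove the inconsistency from the treatment instruction.

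**Conclusion.** The concern holds. As written, the preparation is internally inconsistent in both places: the stated vial and diluent give 5 U/0.1 mL, not 4.

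The possible consequence is 0 to +25% in units applied to Group A. The upper end assumes that staff use 2 mL of diluent and compute volumes at 4 U/0.1 mL; it then applies to every scar up to 32 cm². Between 32 and 40 cm² the excess shrinks to zero if one vial is used per session, and stays at 25% if a second is opened.

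This is not evidence that any patient would be overdosed, and the document does not show which figure is the wrong one. Sample size, error rates and the planned t-tests are unaffected. The point should be fixed because it sits in the operative dosing instruction for a toxin dosed by area.

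**What to change.** Before dosing starts, correct sections 2.2.(b) and 3.2.(b) to a single consistent preparation. There are two options:

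- keep 2 mL of diluent and state 5 U/0.1 mL, which is 0.050 mL per cm² of scar; or
- keep 4 U/0.1 mL and state 2.5 mL of diluent, which is 0.0625 mL per cm² of scar.

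Either gives 2.5 U/cm² up to the cap at 40 cm². The sponsor should confirm which is actually used; the document does not settle it.

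The cost is one figure changed in two places. No extra patients, procedures or data are needed.

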It is a potent neurotoxin that blocks neuromuscular transmission. Some authors have reported that botulinum toxin type A can minimize scar formation by reducing muscle tension during wound healing, causing the fibroblast cell cycle to be paused in a non-proliferative state and influencing TGF- β 1 expression (Lee and Janget., 2018).

1

Statement of the problem:

Does Botulinum toxin type A iontophoresis help in minimizing postburn hypertrophic scars?

Purpose of the study:

The main objective of the study is to evaluate the therapeutic effect of Botulinum toxin type A iontophoresis in improving postburn hypertrophic scars.

Significance of the study:

Hypertrophic scars result from fibroblast proliferation which is responsible for the enhanced collagen production that leads to excessive scarring. By decreasing the tension in the scar, botulinum toxin causes local fibroblasts to gradually change their functional status to proliferate slower, secrete less biologically active mediators and synthesize less extracellular matrix and collagen resulting in the improvement of hypertrophic scars (Elhefnawy., 2016).

One of the most significant drawbacks of BTX-A injection is pain. Iontophoresis, as an alternative modality for drug delivery, has several advantages. It is a painless modality with a reduction of systemic adverse effects due to localized drug administration and its convenience to the patient (Montaser-Kouhsari et al., 2014).

Delimitations:

This study was delimited in the following aspects:

1. Subjects:

Seventy-six patients with postburn hypertrophic scar will be randomly divided into two equal groups each one has 38 patients.

2. Equipment and tools:

2.1. Measurement equipment:

- Sonography (**Reinholz et al., 2016**).
- Patient and Observer Scar Assessment Scale (POSAS) (Reinholz et al., 2016).

2.2. Therapeutic equipment:

• Iontophoretic device.

Hypothesis:

It will be hypothesized that:

Botulinum toxin type A iontophoresis may help in minimizing postburn hypertrophic scars.

Basic Assumptions:

It will be assumed that:

- All patients will receive the same kinds of medication and the same nursing care.
- All subjects are free from any old previous hypertrophic scars.
- All subjects will continue in the study.
- All patients will follow the instructions during the treatment

Definitions of terms:

The following terms are defined for clear understanding of the terminology used in the present study:

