1.1 Design of the study:

In this study, the patients will be randomly assigned into two equal groups (38 patients for each group).

1.1(a) Group A (Study group):

This group includes 38 postburn hypertrophic scar patients who will receive Botox iontophoresis once monthly for 3 months; in addition to their physical therapy program (Positioning, Stretching exercises,

11

Pressure Therapy and Massage) 2 sessions per week for 3 months (Mowafy et al., 2021).

1.1(b) Group B (Control group):

This group includes 38 patients who will receive traditional physical therapy (Positioning, Stretching exercises, Pressure Therapy and Massage) 2 sessions per week for 3 months (Mowafy et al., 2021).

1.2 Criteria for the patient selection:

1.2. a. Inclusion Criteria:

The subject selection will be according to the following criteria:

- Patient with hypertrophic scar (3-6) months after burn healing.
- Age range between 20-40 years.
- Male and female patients will participate in the study.
- All patients have a postburn hypertrophic scar at different body sites.
- All patients enrolled on the study will have their informed consent.

1.2.b Exclusion Criteria:

Exclusion Criteria related to iontophoresis (Sheikh and Dua., 2020):

- Patients with prior medical histories of cardiac arrhythmias.
- Patients with cardiac pacemakers.
- Patients with orthopaedic implants.
- Areas of skin with lesions and impaired sensation.
- During pregnancy and breastfeeding.
- Patient with diabetes mellitus.

Exclusion Criteria related to the delivered drug itself (Elshahed et al., 2020):

- Patients with a history of hypersensitivity or adverse reactions associated with (BTX A).
- Recent BTA administration 6 months before the study.
- Any subject complaining of psychiatric disorders or neurological disorders such as myasthenia gravis.

2-Equipment:

2.1-Measurement equipment:

2.1. (a)Sonography

A high-resolution B-image sonogram of every patient will be taken before and after treatment using an 11-Mhz receiving transducer of Logiq P6 Pro (GE Healthcare, Solingen, Germany). This method allows a good penetration depth of up to 40 mm into the skin and a resolution of around 158 micro m. It has been successfully utilized for objectively measuring pathological scars (**Reinholz et al., 2016**).

2.1. (b) Patient and Observer Scar Assessment Scale (POSAS)

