POSAS is an adequate tool to objectively measure scar quality and the therapeutic success of the applied scar treatment. It consists of two parts; one for the patient (Patient scale; POSAS Patient) and one for the physician (Observer scale; POSAS Observer). Both contain six items on a 10-point rating scale and an extra category "Overall Opinion". All characteristic features of the pathological scars are covered by the questionnaire: vascularity, pigmentation disorders, relief/texture, thickness, pliability, surface area, pain, and itching/pruritus. The latter items, in particular, concern the well-being of the patients (**Reinholz et al., 2016**).

2.2-Therapeutic equipments:

2.2. (a) Iontophoretic device:

Fig. (2): The iontophoresis device (Adapted from Ibrahim et al., 2021).

2.2. (b) Botulinum toxin type A:

• Botox Allergan[®](Irvine, CA, USA) will be used .

It is 100 U vacuum-dried powder in a single-use vial for reconstitution diluted in 2 mL of sterile, preservative-free 0.9% saline to constitute a solution at a concentration of 4 U/0.1 mL) (Elhefnawy et al., 2016).

3-Procedures of the study:

3.1-Measurement procedures:

Both sonography and POSAS will be used for assessment of hypertrophic scar pre treatment and post treatment (after 3 months then after 6 months as follow up).

3.1. (a)Sonography

High frequency ultrasound is the most common used technique for scar assessment. Its inferior resolution compared to optical equivalents is mitigated by its superior penetration depth allowing thickness analysis, even in severe scar thickening. The working mechanism is based on refection of sound waves of structures with different acoustic impedances and the analysis of the refection time to determine the depth of the structure. The penetration depth ranges from the upper dermal layers to full-thickness skin and subcutaneous structures, depending on the employed frequency (Téot et al., 2020).

3.1. (b) Patient and Observer scar Assessment Scale (POSAS):

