The scar will be rated numerically on a ten-step scale by both the patient and doctor on six items: vascularity, pigmentation, thickness, relief, pliability, and surface area on the Observer Scale. The Patient Scale consists of pain, itchiness, color, stiffness, thickness, and irregularity of the scar. One of the reasons POSAS was chosen for scar evaluation is because it is the only scar assessment tool to include a component for patients to fill in. Furthermore, its distinctive feature of reflecting subjective symptoms like pain and pruritus and because of its appropriateness for everyday practice (Kant et al., 2018).

Also, The Arabic version of the (POSAS) is an easy-to-administer, simple, reliable and valid tool for assessment of burn scar and for use on Egyptian population. It is advised to be used in clinical practice as well as scientific researches (Nossier et al., 2018).

15

Observer Scar Assessment Scale

normal skin	1	2	3	4	5	6	7	8	٩	10	worst scar imaginable
Vacantariantian		•	3	•	5	0	,	0		10	worst scar imaginable
vascularization	0	0	0	0	0	0	0	0	0	0	
Pigmentation	0	0	0	0	0	0	0	0	0	0	Нуро 🛛
											Mix 🗆
											Hyper 🛛
Thickness	0	0	0	0	0	0	0	0	0	0	
Relief	0	0	0	0	0	0	0	0	0	0	
Pliability	0	0	0	0	0	0	0	0	0	0	
											+
Total score Observer Scar Scale:											
Patient Scar Assessment Sc	cale	2									
No, no complaints	1	~									
		2	3	4	5	6	7	8	9	10	Yes, worst imaginable
Is the scar painful ?	0	2	3	4 0	5 0	6 0	7 0	8 0	9 0	10 0	Yes, worst imaginable
Is the scar painful ? Is the scar itching?	0	2 0 0	3 0	4 0	5 0	6 0	7 0 0	8 0 0	9 0	10 0	Yes, worst imaginable
Is the scar painful ? Is the scar itching?	0	0	3 0	4 0	5 0	6 0	7 0 0	8 0	9 0	10 0	Yes, worst imaginable
Is the scar painful ? Is the scar itching? No, as normal skin	0 0 1	2 0 0 2	3 0 0 3	4 0 0	5 0 5	6 0 6	7 0 0 7	8 0 0 8	9 0 0 9	10 0 0 10	Yes, worst imaginable Yes, very different
Is the scar painful ? Is the scar itching? No, as normal skin Is the color of the scar different?	0 0 1 0	2 0 2 0	3 0 0 3 0	4 0 0 4	5 0 5 0	6 0 0 6	7 0 7 0	8 0 0 8 0	9 0 0 9	10 0 10	Yes, worst imaginable Yes, very different
Is the scar painful ? Is the scar itching? No, as normal skin Is the color of the scar different? Is the scar more stiff ?	0 0 1 0	2 0 2 0 0	3 0 3 0	4 0 4 0	5 0 5 0	6 0 6 0	7 0 7 0	8 0 8 0	9 0 9 0	10 0 10 0 0	Yes, worst imaginable Yes, very different

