In this study, the descriptive statistics (the mean and the standard deviation) will be calculated for all subjects in all groups of the study to determine the homogeneity of the groups.

Analytical statistics:

Comparison will be made by student's t-test to compare the variables between all groups of the study. Paired t-test was used to compare before and after treatment in the same group. A value of $p \le 0.05$ will be considered statistically significant (Maronna et al., 2006).

Sample size:

Sample size calculation is performed using G*POWER statistical software (version 3.1.9.2; Franz Faul, Universitat Kiel, Germany) based on data of VSS from the previous study (Elshahed et al., 2020) who reported a significant effect of botulinum toxin compared with control in treating hypertrophic scars. The required sample size for this study was 38 subjects per group. Calculations were made using α =0.05, power 90% and effect size = 0.76 and allocation ratio N2/N1 =1.

Test family	Statistical test									
t tests 🗸 🗸	Means: Difference between two independent means (two groups)									
Type of power analy	/sis									
A priori: Compute i	required samp	le size – given α,	power, and effect size	~						
Input Parameters			Output Parameters							
	Tail(s)	Two \vee	Noncentrality parameter δ	3.3284740						
Determine =>	Effect size d	0.7636043	Critical t	1.9925435						
	α err prob	0.05	Df	74						
Power (1-β err prob)		0.9	Sample size group 1	38						
Allocation ratio N2/N1		1	Sample size group 2	38						
			Total sample size	76						
			Actual power	0.9074163						

REFERENCES

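### No primary outcome, primary visit or success rule is named, so the trial-wide error rate is undefined and need not be the 5% behind the sample size

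*Combined protocol and SAP*

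**What the plan says.** - **Hypothesis (opening chapter).** There is one general statement: "Botulinum toxin type A iontophoresis may help in minimizing postburn hypertrophic scars". It names no measure and no time.
- **Measurement procedures (3.1).** Sonography and POSAS are listed together and unranked, before treatment and then "after 3 months then after 6 months as follow up". POSAS has a Patient part and an Observer part (2.1(b)).
- **Sonography (2.1(a), 3.1(a)).** "A high-resolution B-image sonogram of every patient will be taken before and after treatment". The technique is credited with "superior penetration depth allowing thickness analysis", but the variable to be analysed is not stated.
- **Analytical statistics (section 4).** Between groups, Student's "t-test to compare the variables between all groups of the study". Within each group, a paired t-test of before against after. The threshold is p ≤ 0.05 throughout, with no adjustment. The between-group test is not said to use the post-treatment value or the change from baseline.
- **Sample size (sections 1 and 4).** 38 per group, for a single two-sided t-test at 0.05 with 90% power and d = 0.76, taken from VSS data in an earlier study. VSS is not among this trial's measures.

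**The concern.** Normally a reader can recover the claim-bearing test from the hypothesis, the outcome list or the sample size. Here none of the three supplies it: the hypothesis is general, the outcomes are unranked, and the sample size rests on a scale that is not measured.

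The plan therefore has several between-group tests, each at 0.05, and no statement of which result, or how many, would count as showing that the treatment works. It leaves room to choose the outcome, the visit, or post-treatment value versus change after the results are known. A reader of the final report could not tell a planned positive result from a selected one, and the 5% used for the sample size would not describe the risk of a false claim.

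**Working it through.** **1. The plan's own figure.** Inputs from the G*Power output: d = 0.7636043, two-sided α = 0.05, n = 38 per group.
- Noncentrality = d × √(n/2) = 0.7636043 × √19 = 3.3285.
- df = 2 × 38 − 2 = 74; critical t = 1.9925.
- Power from the noncentral t = 0.9074, as printed. With n = 37 it is 0.8998, so 38 is the smallest size that reaches 90%.

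The sample size is arithmetically right, for one test.

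**2. Error if any one significant result counts.** For k tests the error is P(at least one |Z| > 1.96) when there is no effect. If the tests are independent this is 1 − 0.95^k: 9.75% for two, 14.3% for three, 18.5% for four, 26.5% for six. Correlation lowers it. The documents give no correlations, so three settings are assumed: low, middle and high. Between outcomes they are 0.3, 0.7 and 0.9. Where both visits are used, the paired between-visit correlations are 0.5, 0.8 and 0.9, and the two are multiplied across outcome and visit. Results are from simulated normal test statistics.

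| Tests | Low | Middle | High |
|---|---|---|---|
| 2: sonography, POSAS; 3 months | 9.5% | 8.3% | 7.1% |
| 3: sonography, Patient, Observer; 3 months | 13.6% | 11.0% | 8.4% |
| 4: the two outcomes, both visits | 16.9% | 12.8% | 9.8% |
| 6: the three scores, both visits | 23.9% | 16.5% | 11.5% |

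Simulated t-tests with 38 per group agree for three tests: 13.9%, 11.2% and 8.5%. The two-visit rows depend on the chosen pairs: with 0.3 for both correlations, six tests give about 25%.

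False claims of benefit alone are about half of each figure, to be set against a nominal 2.5%: 3.5-4.8% for two tests, 4.2-6.8% for three, about 6-12% for six.

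**3. Error if both sonography and POSAS must succeed at 3 months.** P(both |Z| > 1.96) is about 0.5% at correlation 0.3, 1.7% at 0.7 and 3.0% at 0.9.

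**4. Post-treatment value or change.** For one outcome at one visit, with equal variances and pre/post correlation ρ, the two test statistics correlate at √((1 − ρ)/2). For ρ = 0.3, 0.5, 0.7 and 0.8 this is 0.59, 0.50, 0.39 and 0.32. The chance that at least one is significant is 8.8%, 9.0%, 9.3% and 9.5%. Naming outcome and visit without naming the analysis therefore still leaves about 9-10% if the better result is reported.

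**5. Power of the remedies at 38 per group, unadjusted t-test.**
- One primary at 0.05: 0.907 at d = 0.7636, 0.733 at d = 0.6, 0.576 at d = 0.5.
- Alpha split over three co-equal outcomes (0.05/3), d = 0.7636: 0.808.
- One primary at 0.05 plus two Holm-adjusted secondaries tested whatever the primary shows: overall error about 9% at correlation 0.3 and 6% at 0.9. The secondaries must therefore wait for the primary.

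**The case against.** The strongest objection is that the inflation depends on a rule the plan does not contain. Nowhere does it say that one significant variable is enough. It says that both sonography and POSAS will be used, which fits reading them together, and on that reading the error is below 5% (step 3). This stands. A reader might infer that the trial has a 14% or 24% false-positive rate; the documents do not support that. They support only that the rate is undefined, with values on both sides of 5% depending on the unstated rule.

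Second, the wording leans towards 3 months: sonograms are before and after treatment, and 6 months is called follow-up. That is fair, but the plan does not make 3 months primary, and two or three tests would remain there in any case.

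Third, sonographic thickness is clearly implied. It would be too strong to say that the plan gives no hint of the sonographic variable. What is missing is a statement that thickness is the variable analysed.

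A reader might also be tempted to count more tests, because of POSAS "Both contain six items on a 10-point rating scale and an extra category" for the overall opinion. That passage describes the instrument. Nothing says that single items or overall opinions will be tested, so they are not counted here.

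Finally, part of the opening of the document was not available. The statement about absence is limited to the text reviewed, which includes the whole chapter on subjects, measurements and statistics.

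**Conclusion.** The point holds in conditional form. The plan names no primary outcome, primary visit or success rule, and its sample size covers one test on a scale it does not measure. The trial-wide error is therefore not defined. It is about 7-14% if any one of two or three tests at 3 months suffices, about 10-24% if any one of four to six tests over both visits suffices, and about 0.5-3% if sonography and POSAS must both succeed at 3 months. All three ranges rest on assumed correlations. The sample-size arithmetic is not in question, but whether its d applies to any outcome of this trial is unknown. This should be corrected because it decides how the main claim can be read.

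**What to change.** Before anyone sees outcome data by group:

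- Name one primary outcome at one visit, for example sonographic scar thickness at 3 months. The investigators may prefer another.
- Analyse it between groups at two-sided 0.05 by ANCOVA with its baseline value as covariate. The baseline is already collected, and this settles the choice between post-treatment value and change.
- Make the other scores and all 6-month results secondary: either tested with Holm adjustment only if the primary is significant, or labelled exploratory.
- State that the efficacy claim does not rest on the within-group paired t-tests, which do not compare the treatments.
- State that the 0.907 power at 38 per group applies to this primary only if d = 0.76 from VSS carries over, and give the values at d = 0.6 and 0.5 from step 5.

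**Cost.** A few sentences in the statistical section and no extra patients. The pages carry an approval date of 17/5/2022, so a formal amendment may be needed; the documents do not say how far the trial has progressed. The price is that secondary results cannot carry the main claim alone, and a thickness primary does not capture pain or itch. Splitting alpha over three co-equal outcomes would avoid ranking them, but lowers power from 0.907 to 0.808 at the planned effect size.
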